Evaluating endothelial dysfunction by assessing coronary vascular function can thus not only index the adverse impact of multiple risk factors but also provide the opportunity to evaluate the benefit of an intervention which targets coronary vascular dysfunction. The synthesis and release of nitric oxide (NO) is an essential component of normal endothelial function. NO’s downstream effects include not only vasodilation and a resultant increase in coronary flow, but also anti-proliferative, anti-coagulant, anti-adhesive, and anti-inflammatory effects⁵. Its beneficial vascular effects are mediated by stimulation of the soluble guanylyl cyclase (sGC) enzyme, which converts guanosine-5'-triphosphate (GTP) to the second messenger guanosine monophosphate (cGMP). cGMP activates GMP-dependent protein kinases (PKG) which in turn phosphorylate several proteins that have vasorelaxant and anti-atherosclerotic effects⁶. Reduced bioavailability of NO associated with endothelial dysfunction, therefore, leads to loss of its important downstream effects, and therefore may be one of the important mechanisms responsible for progression of atherosclerosis and its associated adverse clinical outcomes⁷.

Date: June 3, 2025

Principal Investigator: [name]., PhD.

Application Number: IRB00310207

Hypothesis: Vericiguat improves coronary vascular endothelial function in patients with metabolic syndrome or type 2 diabetes mellitus and impaired coronary vascular function.

We will perform a placebo-controlled, randomized, double-blind study to test the hypothesis, that the administration of vericiguat, which increases soluble guanylate cyclase (sGC) activity despite low NO, improves coronary vascular function in patients with the metabolic syndrome or type 2 diabetes mellitus and coronary vascular dysfunction. We will be using MRI studies to evaluate coronary vascular function in response to study drug administration.

2. Objectives

(include all primary and secondary objectives)

Primary Objective:

1. To characterize the impact of vericiguat on global (micro- and macro- vascular function) coronary vascular function by comparing the responses prior to, and following, vericiguat administration, to isometric handgrip exercise, an endothelial-specific stressor in patients with the metabolic syndrome or type 2 diabetes mellitus and baseline coronary vascular dysfunction.

Secondary Objective:

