1. To compare changes in resting, pre-isometric hand exercise (IHE), coronary blood flow before and following study drug administration within and between the vericiguat and placebo groups.
2. To compare coronary flow and cross-sectional area prior to the isometric handgrip exercise before, and following study drug administration within and between the vericiguat and placebo groups.
3. To obtain serum, plasma, and urine laboratory studies to characterize markers/mediators of inflammation and of the nitric oxide signaling pathway prior to and following up-titration of the study drug.

3. Background

(briefly describe pre-clinical and clinical data, current experience with procedures, drug or device, and any other relevant information to justify the research)

Coronary vascular function can be assessed by examining changes in coronary blood flow and dimension following initiation of a coronary endothelial-dependent stimulus. If function is normal, the stimulus results in a significant increase in coronary blood flow and dimension, but if abnormal, the result is only a small, or no, increase, or even a decrease. These changes were previously assessed via placement of a catheter within the studied artery⁸. Because that procedure is invasive, the associated risks did not justify most studies in individuals without known or suspected significant stenoses or in the serial studies required to assess the benefit of an intervention designed to improve coronary vascular function. The Hopkins investigator team for this proposed study, however, has extensive experience in using MRI methodology to non-invasively and safely study coronary vascular function in healthy individuals⁹ and in those with pro-inflammatory states¹⁰ and coronary disease¹¹ and to perform serial studies to assess the impact of interventions¹².

Date: June 3, 2025

Principal Investigator: [name]., PhD.

Application Number: IRB00310207

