 - fasting high-density lipoprotein (HDL) cholesterol level < 40 mg/dL in men or < 50 mg/dL in women
 - fasting blood glucose > 100 mg/dL or HbA1c $\geq 5.7\%$
- Either one of the following:
 - Men ≤ 40 or women ≤ 50 years of age with no history or symptoms of ischemic heart disease, or
 - Men >40 or women >50 years of age with either one of the following:
 - a coronary angiography (including CT angiography) within the past 36 months showing no significant coronary artery disease in at least one major coronary artery, defined as $>50\%$ stenosis of the left main coronary artery and/or $>70\%$ stenosis of another major coronary vessel, or
 - a coronary artery calcium score obtained within the prior 36 months or if no prior calcium scan, one performed as a research study following consent with a score ≤ 10 in at least one major coronary artery.
- IHE-induced %-change in coronary flow < or equal to 13%

Exclusion Criteria:

- Systolic blood pressure <110 mm Hg
- Current or anticipated use of long-acting nitrates, a sGC stimulator, or phosphodiesterase type 5 (PDE5) inhibitors
- Hematocrit $<30\%$
- Unable to understand the risks, benefits, and alternatives of participation so as to provide informed consent
- Women who are pregnant.
- Women who are breastfeeding
- Women with reproductive capacity not using an acceptable form of contraception
- History of claustrophobia
- Inability to lie flat and still for 45 minutes

- Presence of non-MR-compatible objects or devices, such as intra-orbital debris, intra-auricular implants, intra-cranial clips, an implanted defibrillator or a pacemaker
- History as a machinist, welder, metal worker or a similar activity that poses the risk of metal exposure to the eyes

6. Drugs/ Substances/ Devices

a. *The rationale for choosing the drug and dose or for choosing the device to be used.*

As detailed above, we propose using vericiguat to “bypass” the requirement for nitric oxide synthesis in an attempt to improve endothelial function and hence coronary vascular function in individuals with preexisting dysfunction²⁷. If successful, a sGC-directed prevention strategy may improve coronary vascular function and decrease cardiovascular risk. The dose and titration described to reach the dose is that used for patients with heart failure and approved by the FDA to treat those patients²⁸.

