b. *Justification and safety information if FDA approved drugs will be administered for non-FDA approved indications or if doses or routes of administration or participant populations are changed.*

Vericiguat is approved for reducing the risk of cardiovascular death and heart failure hospitalization following hospitalization or need for outpatient intravenous diuretics in adults with symptomatic chronic heart failure and ejection fraction less than 45%. The dose and route of administration are the same as that administered for this FDA approved indication. The dose is not changed from that used for the marketed drug.

c. *Justification and safety information if non-FDA approved drugs without an IND will be administered.*

We will be using an FDA approved drug.

7. Study Statistics

a. *Primary outcome variable.*

In a paired analysis, we hypothesize that there is a significant change in coronary flow and dimension with isometric handgrip exercise (IHE) in the group randomized to vericiguat from that measured at baseline, prior to the initiation of vericiguat, to that measured following vericiguat administration and up-titration. We will be using either a paired student t-test or a Wilcoxon test to examine this hypothesis.

In unpaired analyses, we hypothesize that the change in the vericiguat group from baseline to post-up titration will be greater than the change in the placebo group. We will be using either an unpaired student t-test or a Mann-Whitney test to examine this hypothesis

b. *Secondary outcome variables.*

We will conduct bivariate analyses to compare markers/mediators of inflammation and that of the nitric oxide pathway.

Other exploratory outcome variable that we are interested in include age, sex, and race. We will be using parametric and non-parametric tests for continuous variables and chi-square or Fisher's exact tests for categorical variables.

c. *Statistical plan including sample size justification and interim data analysis.*

Date: June 3, 2025

Principal Investigator: [name]., PhD.

Application Number: IRB00310207

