All sample size calculations are based on 80% power and 5% alpha error for two-sided tests. We have prior studies with small sample sizes to inform our baseline expectations¹². For our primary analysis, our minimum expected difference in change in coronary flow with IHE in the vericiguat group with our planned sample size of n=30 in the vericiguat group, allowing for 10% loss to follow-up at 8 weeks (n=27 remaining), with 80% power and an alpha of 0.05 is $7.8\% \pm 13.6\%$. The detectable effect size at 90% power is $9.1\% \pm 13.6\%$. (Figure 3).

[figure not shown]

Figure 3: Power and sample size calculated for estimated difference in change in coronary flow with IHE from baseline to 8 weeks in the vericiguat group

The study investigators will be responsible for analyzing the study data to assess the completeness of data collection, to assess any adverse events, and to identify any findings which may have clinical relevance. This will be performed while maintaining the blind. A Data Safety and Monitoring Committee will review and, if necessary unblind, the data when the outcomes of the first third (n=15) of the anticipated enrolled participants are available and at the end of the study. This committee may request to review/audit the data at any time.

The data will be maintained in a REDCap database.

The data will be unblinded following the completion of the protocol, and medical/scientific review has been completed, protocol violators have been identified and data has been declared complete, although the Hopkins Institutional Review Board and Data Safety and Monitoring Committee may request prior unblinding.

Date: June 3, 2025

Principal Investigator: [name]., PhD.

Application Number: IRB00310207

The routine safety laboratory studies will be analyzed within 48 hours of collection.
The MRI data will be analyzed within two months of each study

d. Early stopping rules.

The study will be stopped early on the recommendation of the Data Safety and Monitoring Committee or if there is any new published information regarding the safety of the study drug or the study procedures.

8. Risks

a. Medical risks, listing all procedures, their major and minor risks and expected frequency.

Study Drug:

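### The only analysis called primary and sized is a before-after change in the vericiguat arm, in people selected for a low value on that baseline scan; the placebo comparison has no rank or power

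*Combined protocol and SAP*

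**What the plan says.** - **Section 2, primary objective.** The effect of vericiguat on global coronary vascular function is to be characterised "by comparing the responses prior to, and following, vericiguat administration, to isometric handgrip exercise". Placebo is not mentioned. Secondary Objective 1, by contrast, compares "coronary blood flow before and following study drug administration within and between the vericiguat and placebo groups".
- **Section 7a, primary outcome variable.** Two hypotheses stand under this heading. The first is that in the vericiguat group "there is a significant change in coronary flow and dimension with isometric handgrip exercise (IHE"), with the test given as "We will be using either a paired student t-test or a Wilcoxon test to examine this hypothesis". The second is between arms: "we hypothesize that the change in the vericiguat group from baseline to post-up titration will be greater than the change in the placebo group". Nothing says which of the two decides the trial.
- **Section 7c, sample size.** The text reads "For our primary analysis, our minimum expected difference in change in coronary flow with IHE in the vericiguat group", with 30 enrolled, 27 remaining after 10% loss, and a detectable difference of 7.8% ± 13.6% at 80% power (9.1% at 90%). The Figure 3 caption also refers to the vericiguat group only. The 15 placebo participants enter no calculation.
- **Section 5, inclusion.** Entry requires "IHE-induced %-change in coronary flow < or equal to 13" per cent.
- **Section 4a, sequence.** The screening MRI comes first, then echocardiogram and laboratory studies, then 2:1 randomization. A second screening MRI is only for technical problems. The next MRI follows the drug period.

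**The concern.** A paired test within one arm answers whether the reading changed. It cannot by itself show that vericiguat caused the change, which is what the primary objective asks. Selection makes this worse here. Participants enter because their measured flow response was low, and the same measurement is then the starting point for the change. Some of those low readings are low partly through measurement error, and on repeat they move back up. Both randomized arms share that rise, so the between-arm difference removes it and the paired difference does not.

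At stake is which result counts as the trial's answer. With two unranked tests, a significant paired result beside a non-significant placebo comparison could be reported as meeting the primary analysis, although regression to the mean alone could produce it. The point concerns flow. Entry is not truncated on cross-sectional area, so no bias figure is claimed for dimension.

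**Working it through.** **1. The plan's own figure.** Inputs from 7c: n = 27, two-sided 5%, and ± 13.6% read as the SD of the paired change (an inference). Noncentrality = difference × √27 / 13.6.
- 7.8: 7.8 × 5.196 / 13.6 = 2.98, power 81.8%.
- 9.1: 9.1 × 5.196 / 13.6 = 3.48, power 91.7%.

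The stated figures therefore fit a one-arm paired test.

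**2. Expected rise with an inert drug.** Let the screened population have mean μ and SD s, and let SDd be the retest SD of change between two scans of an untreated person. Error variance per scan is SDd²/2, so reliability = 1 − SDd²/(2s²). With c = (13 − μ)/s, selecting readings at or below 13 gives

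rise = (SDd²/2)/s × φ(c)/Φ(c).

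The documents give none of μ, s or SDd. I assumed μ of 5, 10, 15; s of 12, 15, 20; SDd of 7, 10, 13.6 (27 combinations).

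Example, μ = 10, s = 15: c = 0.2 and φ/Φ = 0.391/0.579 = 0.675.
- SDd 7: 24.5/15 × 0.675 = 1.10 points.
- SDd 10: 50/15 × 0.675 = 2.25 points.
- SDd 13.6: 92.48/15 × 0.675 = 4.16 points.

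**3. False benefit with an inert drug.** Simulated trials; upper tail of a two-sided 5% test, nominal 2.5%; 27 on vericiguat, 13 on placebo.

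| Retest SD | Rise (points) | Paired test declares benefit | Between-arm test declares benefit |
|---|---|---|---|
| 7 | 0.7-1.9 | about 7-27% | about 2.5% |
| 10 | 1.4-3.8 | about 11-52% | about 2.5% |
| 13.6 | 2.6-7.0 | about 17-83% | about 2.5% |

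Over all 27 combinations the between-arm upper tail was 2.2-2.7% by unpaired t, Welch or ANCOVA. The Mann-Whitney test stayed at about 1.8-2.8%. The worst corner (SDd 13.6, s = 12) implies a reliability of 1 − 92.48/144 = 0.36.

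**4. What the between-arm test can detect.** Applying 10% loss to 15 gives 13.5, so 27 versus 13 or 14. The vericiguat SD is taken as 13.6. The placebo SD is an assumption: in the null model the SD of change after selection is 6.8-6.9, 9.4-9.8 and 12.0-13.2 for retest SDs of 7, 10 and 13.6.

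| Placebo SD | Test | Power for 7.8 points | Detectable at 80% (points) |
|---|---|---|---|
| 13.6 | pooled t | 38-40% | 12.9-13.2 |
| 10 | Welch | 51-53% | 10.8-11.0 |
| 7 | Welch | 64-66% | 9.3-9.4 |

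Example, 27 v 13 with both SDs 13.6: standard error = 13.6 × √(1/27 + 1/13) = 4.59; 7.8/4.59 = 1.70; power 38%. If the planned Student test pools variances, power for 7.8 falls to 43-45% at placebo SD 10 and 47-50% at placebo SD 7. In the SD 7 case its actual two-sided size is only 1.8-2.0%.

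**The case against.** The strongest reply is that the control is planned. Section 2 of the plan sits under a placebo-controlled, double-blind design, section 3 promises a comparison with placebo, and section 7a names the between-arm test under the primary heading. This stands: the defect is missing rank and power, not a missing comparison. It does not remove the problem, because 7c reserves the term primary analysis, and all the power, for the one-arm test.

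The second reply is that the size of the bias is assumption. That also stands. A range of 7% to 83% cannot be narrowed from the documents, and section 4a's claim of good reproducibility over eight weeks favours the mildest row. There the rise is modest against 7.8 points, but false benefit is still about 3 to 11 times nominal (7/2.5 to 27/2.5).

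Three narrower points are fair:
- The primary objective names global function; only 7c names flow as the primary-analysis variable.
- The 7.8 points come from what 27 people can show in a paired test. The documents do not justify them as a between-arm target.
- In the null model, baseline adjustment reduces the SD of change by only 0.5-11%. If response to the drug depends on baseline, the gain could be larger.

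Requiring both tests to succeed would also block a claim based on regression alone. It would still need the between-arm power to be stated.

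**Conclusion.** The concern holds and should be fixed before unblinding. The plan sizes and labels as primary a one-arm change that takes in regression to the mean, and leaves the comparison that removes it without rank or power.

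Confidence is high on the designation and on the direction of bias. The direction needs only measurement error and the reading, from section 4a, that the qualifying scan is the baseline; no other pre-treatment MRI is described. The size of the bias rests on the assumed μ, s and retest SD. The between-arm detectable differences rest on reading 13.6 as the SD of change and on an assumed placebo SD.

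**What to change.** **Needed**
- In the primary objective, 7a and 7c, name vericiguat versus placebo on the IHE-induced percentage change in coronary blood flow as the single primary test at two-sided 5%. Report within-arm changes descriptively, and align the within-group wording of the secondary objectives with that.
- In 7c, replace 7.8% and 9.1% as the primary-analysis figures with the between-arm detectable difference at 27 versus 13-14, and state the SD assumed in each arm.
- State the retest SD from the reproducibility work cited in section 4a. It would show which row of the bias table applies.

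**Consequences to write down**
- Dimension (cross-sectional area), now in the 7a primary hypothesis, becomes secondary. The IHE-induced area change must then be added to the secondary objectives and 7b, because Secondary Objective 2 is limited to values before the handgrip: "To compare coronary flow and cross-sectional area prior to the isometric handgrip exercise before, and following study drug administration".
- Fix one between-arm method in advance. ANCOVA on baseline is preferable. The planned unpaired test of change also controls the error, but should use an unequal-variance form.

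**Cost.** No new participants, visits or scans: the placebo arm and the unpaired test are already planned. Dimension loses its primary place. The power statement becomes less favourable: about 38-66% for 7.8 points across the placebo SDs considered, against 81.8% for the paired test. No added enrolment is proposed; the plan should simply state what the trial can detect.
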